12.5 Total volume of blood removed

The maximum total volume of blood taken from any volunteer in the trial will be about 175 mL, as stated in Table 14 (Part A), Table 15 (Part B), Table 16 (Part C). Additional blood samples for assay of BEN8744 or for laboratory safety tests may be taken as described in section 12.2. No more than an extra 50 mL of blood will be taken from any subject.

Table 14: Planned blood volume (Part A)

Test	Planned number of tests	Volume (mL)	Total planned blood volume (mL)
Haematology	6	2.7	16.2
Clinical chemistry/serology/pregnancy/FSH	6	4.0	24
Pharmacokinetics	15	2.7	40.5
Discard (when using a cannula)	12	1	12
		Total	92.7 mL

Table 15: Planned blood volume (Part B)

Test	Planned number of tests	Volume (mL)	Total planned blood volume (mL)
Haematology	10	2.7	27
Clinical chemistry/serology/pregnancy/FSH	10	4.0	40
Pharmacokinetics	30	2.7	81
Discard (when using a cannula)	24	1	24
		Total	172 mL

Table 16: Planned blood volume (Part C)**Once-daily dosing**

Test	Planned number of tests	Volume (mL)	Total planned blood volume (mL)
Haematology	7	2.7	18.9
Clinical chemistry/ serology/pregnancy/FSH	7	4.0	28
Pharmacokinetics	31	2.7	83.7
Discard (when using a cannula)	22	1	22
		Total	152.6 mL

Twice-daily dosing

Test	Planned number of tests	Volume (mL)	Total planned blood volume (mL)
Haematology	7	2.7	18.9
Clinical chemistry/ serology/pregnancy/FSH	7	4.0	28
Pharmacokinetics	37	2.7	99.9
Discard (when using a cannula)	28	1	28
		Total	174.8 mL

13 Trial materials**13.1 Identity of test product(s)**

Size 0 Swedish orange capsules containing 2 mg, 10 mg, and 40 mg BEN8744 and matching placebo capsules contain excipients only, will be provided to the HMR Pharmacy by Quotient Sciences Ltd (Reading, UK). The capsules are packaged in high density polyethylene (HDPE) bottles with child-resist polypropylene (PP) twist-off cap.

Full details of BEN8744 and placebo formulations are included in the IB²⁹ and Investigational Medicinal Product Dossier (IMPD)³⁶.

The sponsor will provide to HMR a certificate of analysis (CoA), and a Certificate of GMP Compliance (CoC) for the test product for HMR's Qualified Person to release batches of IMP.

13.2 Packaging and labelling

The trial medication will be packaged and labelled by the HMR Pharmacy, in accordance with The Rules Governing Medicinal Products in the European Union, Volume 4: Good Manufacturing Practice (GMP), and with HMR's Manufacturing Authorisation for IMPs (MIA(IMP)). The IMP labels will include all the information required by Annex 13 to GMP³⁷.

13.3 Storage and accountability of IMP

The IMP will be stored and accounted for according to GMP and HMR SOPs.

At the end of the trial, all unused IMP supplies will be returned to the sponsor or destroyed in accordance with the sponsor's instructions.

14 Adverse events

14.1 Definitions of adverse events

Adverse event (AE)

Any untoward medical occurrence in a patient or clinical trial subject administered a medicinal product and which does not necessarily have a causal relationship with that treatment.

Adverse drug reaction (AR)

All untoward and unintended responses to an IMP related to any dose administered. Note that, according to the ICH Guideline for Good Clinical Practice (ICH GCP), the phrase 'response to an IMP' means that a causal relationship between the medicinal product and an AE is at least a reasonable possibility, ie a relationship cannot be ruled out.

Unexpected AR

An AR, the nature or severity of which is not consistent with the applicable product information (eg IB for an unauthorised investigational product, or summary of product characteristics for an authorised product).

Serious adverse event (SAE) or serious adverse drug reaction (SAR)

An AE or AR that:

- is fatal;
- is life-threatening;

- requires inpatient hospitalisation, or prolongs existing hospitalisation;
- results in persistent or significant disability or incapacity; or
- is a congenital anomaly or birth defect.

Note that:

- the term 'life-threatening' in the definition of 'serious' refers to an event or reaction in which the patient was at risk of death at the time of the event; it does not refer to an event or reaction which hypothetically might have caused death had it been more severe; and
- in accordance with the ICH Guideline on Clinical Safety Data Management: Definitions and Standards of Expedited Reporting, events or reactions that are not immediately life-threatening or may not result in death or hospitalisation, but might jeopardise the subject or require intervention to prevent one of the other outcomes listed above, should usually be considered serious.

Significant AE or AR

Any SAE or SAR, or an AE or AR which is not serious but is otherwise significant. The following should normally be considered significant:

- a marked haematological or other laboratory abnormality;
- an AE or AR that leads to an intervention, including withdrawal of drug treatment, dose reduction or significant additional concomitant therapy; or
- any AE or AR that the investigator considers to be significant.

14.2 Procedures for recording adverse events

Subjects will be carefully monitored for AEs. The investigator or delegate will question the subjects about AEs using a non-leading question, such as 'How are you feeling?'. The investigator will also record AEs reported spontaneously by the subjects. Clinically significant changes in the findings of physical examination, and clinically significant abnormalities in the results of objective tests (eg laboratory variables, x-ray, ECG) may also be recorded as AEs. The investigator will use the following criteria when deciding whether to report an abnormal result as an AE.

1. The test result is associated with accompanying symptoms.
2. Results of additional diagnostic tests cause concern or necessitate medical intervention.
3. As a consequence of the test result, the dose administered to the subject is changed, the subject is withdrawn, or the subject is given concomitant treatment.
4. The investigator considers the result to constitute an AE.

If any of the above criteria are met, the investigator will report the result as an AE.

A record will be kept in the source documents of all AEs as reported, whether believed to be related or unrelated to the treatment. The record will include the following.

- **Clinical symptoms:** a simple, brief description.
- **Date and time of onset and end:** of clinical symptoms.
- **Frequency:** constant or intermittent.
- **Severity.** The following categories will be used:

Mild: the AE does not interfere with the volunteer's daily routine, and does not require intervention; it causes slight discomfort.

Moderate: the AE interferes with some aspects of the volunteer's routine, or requires intervention, but is not damaging to health; it causes moderate discomfort.

Severe: the AE results in alteration, discomfort or disability which is clearly damaging to health.

- **Relationship to treatment:** The assessment of relationship of AEs to the administration of IMP is a clinical decision based on all available information at the time of the completion of the case report form. The following categories will be used.

Possibly related

- An event for which, after careful medical evaluation, a connection with trial medication cannot be ruled out with certainty. The event occurs after exposure to trial medication. The event may occur at a reasonable time in relation to the time of administration of the trial medication, but might also be attributable to a commonly occurring alternative cause. Alternatively, the event may not occur at a reasonable time in relation to the time of administration of trial medication, but may not be attributable to an alternative cause.

Unlikely to be related

- An event which occurs before exposure to the trial medication, or which does not occur at a reasonable time in relation to the time of administration of trial medication, and can be attributed to a commonly occurring alternative cause. Alternatively, the event is unrelated to the trial (eg road traffic accident), unless it can be demonstrated that the treatment could have caused the event.
- **Action taken:** none, drug treatment, subject withdrawn, other (specified).
- **Outcome:** recovered/resolved, recovering/resolving, not recovered/not resolved, or unknown.

14.3 Procedures for dealing with serious adverse events

In the event of any SAE which, in the investigator's opinion, justifies termination or modification of the trial (see section 8.4), dosing will be stopped and the sponsor's medical monitor will be informed immediately (within 24 h of the investigator becoming aware of the event) by telephone or email, as follows.

Medical monitor: [name]
[contact]
Email: [contact]

All SAEs occurring after the signing of the ICF until the follow up visit, regardless of study drug relationship, must be reported to the sponsor's pharmacovigilance provider, with as much information as possible, within 24 h of the investigator becoming aware of the event. The investigator will complete an SAE form and provide it to the sponsor's pharmacovigilance provider, via the following contact details.

QbD Group Ltd
Email (primary): [contact]
Tel (back-up): [contact]

The sponsor will also be notified by email ([contact]).

The investigator will notify the REC of SAEs that occur during this trial, if applicable, in accordance with the SOPs issued by the Research Ethics Service (RES)³⁸.

The sponsor is responsible for determining the expectedness of the event, using the reference safety information in the IB²⁹. The sponsor will notify the MHRA of all suspected unexpected serious adverse reactions (SUSARs), and will be responsible for ensuring that the REC is notified of SUSARs, if applicable. SUSARs that are fatal or life-threatening must be notified to the MHRA and REC within 7 days after the sponsor has learned of them. Other SUSARs must be reported to the REC and MHRA within 15 days after the sponsor has learned of them.

14.4 Procedures for handling withdrawals due to adverse events

The investigator will assess the reason for withdrawal as far as possible and will fully record the circumstances and medical details. Provided that subjects give written informed consent, they will undergo the standard medical examination and laboratory tests at withdrawal from the trial which they would have undergone had they completed it (see also section 9.4).

14.5 Procedures for reporting pregnancies

Subjects will be asked to follow the contraception guidance in section 11.

If, during the study, the investigator becomes aware of a pregnancy in a subject or their partner, they will inform the sponsor's pharmacovigilance provider immediately (within 24 h of the investigator becoming aware of the event), as follows.

QbD Group Ltd

Email (primary): [contact]

Tel (back-up): [contact]

The investigator will follow-up the pregnancy according to HMR SOPs, provided the subject (or their partner) consents to that. A pregnancy will not constitute an SAE unless it meets one of the criteria in section 14.1.

15 Data management and quality assurance

Paper source documents will be securely stored within HMR. Data collected in source documents (see section 18.2) will be transcribed into an electronic CRF (eCRF).

The investigator is responsible for ensuring the accuracy and completeness of the data entered into the eCRF, and the timeliness of data entry. Clinical data (including AEs, concomitant medication, etc) will be entered into a 21 CFR Part 11-compliant Medrio M-1 database. The Medrio M-1 system includes password protection and internal quality checks, such as automatic range checks, to identify data that appear inconsistent, incomplete, or inaccurate. Data reported in the eCRF, derived from source documents, should be consistent with the source documents or the discrepancies should be explained. Where the data violate data validation checks, queries will be generated for resolution by clinical staff. All edits made to the database upon resolution of queries will be recorded in an electronic audit trail.

The database will be locked after the following have been completed: all expected eCRF data have been entered and accounted for; all discrepancies have been resolved; data have been coded as appropriate; SAEs have been reconciled; all site audit findings impacting the database have been closed; and QC inspection has been completed.

Data in source documents will be checked by the HMR Quality Assurance (QA) Department. In addition, the HMR QA Department will audit the trial report; that audit will include checks to ensure that statistical output is correctly reproduced in the report. If requested, the investigator will provide the sponsor, MHRA, and REC with direct access to the original source documents.

16 Statistical methods

16.1 Pharmacokinetic methods

The pharmacokinetic analysis will be done by the Statistics and Data Management Department at HMR, using WinNonlin 8.3 or higher.

Actual times will be used to derive pharmacokinetic parameters. Missing data will not be imputed.

For calculation of all PK parameters, and for individual concentration–time plots, plasma concentrations below the limit of quantification of the assay (BLQ) will be treated as follows: values that occur before t_{\max} will be taken as zero; all other values will be taken as missing.

For calculation of plasma concentration summary statistics, BLQ values will be taken as zero, unless they fall between two quantifiable concentrations, in which case they will be treated as missing.

For urine concentrations reported as BLQ, it is not possible to impute a value. The amount excreted will be set to zero when the concentration is BLQ.

The pharmacokinetic parameters listed in sections 16.1.1 and 16.1.2 will be derived.

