8.1.3 Part C

Enrolment of up to 32 healthy subjects is planned, in up to 3 groups (Groups C1–C3) and 1 optional group (Group C4). Each group will consist of 8 subjects.

Each subject will receive daily doses of BEN8744 or placebo, by mouth, for 14 days. At each dose level, 6 subjects will receive BEN8744 and 2 will receive matching placebo. Doses will be taken once or twice daily in the fasted state, unless emerging data indicate they should be taken in the fed state.

[figure not shown]
Part C will not start until at least 3 dose levels have been completed in Part A, as described in section 8.5.4. Part C may also be conducted in parallel with Part B. The dose, dosing regimen (once or twice daily), and whether the dose is taken fed or fasted, will be determined based on review of the available safety, tolerability and PK results from Parts A and B, and previous groups in Part C, as described in section 8.5.

The first total daily dose (ie, morning plus evening dose, if a twice-daily dosing regimen is chosen) tested in Part C (Group C1) will be the same as, or lower than, a single dose that has been given in Part A without any safety concerns. See also section 8.5.

[figure not shown]
[figure not shown]
[figure not shown]
Subjects will be screened within 28 days before their first dose of trial medication. Subjects will be resident on ward from the day before their dose (Day -1) until up to 72 h after their final dose (Day 17). They will return for a follow-up visit 7 (± 2) days after their inpatient stay (Day 24 ± 2 days).

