8. Vital signs consist of: supine systolic and diastolic blood pressure, pulse rate, tympanic temperature and respiratory rate. During the period of residence, they will be assessed at the following timepoints on Days 1 and 14: predose, 2, 4, 8 and 12 h postdose. Predose vital signs (including on Days 2–13) should be measured up to 90 min before dosing. If twice-daily dosing, vital signs should be measured before the morning dose only.
9. Triplicate measurements (obtained ≥ 2 min apart) will be made at screening. Single measurements will be made at all other timepoints. Measurements should be made with subjects in a supine position, after resting for 5 min.
10. During the period of residence, ECGs will be recorded at the following timepoints on Days 1 and 14: predose, 2, 4, 8 and 12 h postdose. Predose ECGs (including on Days 2–13) should be done up to 2 h before dosing. If twice-daily dosing, ECGs should be done before the morning dose only.
11. Triplicate ECG recordings (made ≥ 2 min apart) will be made at screening; single recordings will be done at all other timepoints. Recordings should be made with subjects in a supine position, after resting for 5 min.
12. Once-daily dosing: Days 1 and 14 at predose and postdose at 0.25, 0.5, 1, 2, 3, 4, 6, 8, and 12 h; on Days 2 (24 h) and Day 15 (24 and 36 h); on Day 16 (48 h); and on Day 17 (72 h). Trough samples will be taken predose on Days 3, 5, 7, 9, 11, and 13.
13. Twice-daily dosing: Day 1 and 14 at predose, and postdose at 0.25, 0.5, 1, 2, 3, 4, 6, 8, and 12 h (pre-evening dose on Day 1); on Day 1 at 12.5, 13, 14, 15, and 16 h; Days 2 (20 and 24 h) and Day 15 (24 and 36 h); on Day 16 (48 h); and on Day 17 (72 h). Trough samples will be taken pre-morning dose on Days 3, 5, 7, 9, 11, and 13.
14. Blood samples for assay of BEN8744 will be taken on:

 - Once-daily dosing: Days 1 and 14 at predose and postdose at 0.25, 0.5, 1, 2, 3, 4, 6, 8, and 12 h; on Days 2 (24 h) and Day 15 (24 and 36 h); on Day 16 (48 h); and on Day 17 (72 h).
 - Twice-daily dosing: Day 1 and 14 at predose, and postdose at 0.25, 0.5, 1, 2, 3, 4, 6, 8, and 12 h (pre-evening dose on Day 1); on Day 1 at 12.5, 13, 14, 15, and 16 h; Days 2 (20 and 24 h) and Day 15 (24 and 36 h); on Day 16 (48 h); and on Day 17 (72 h). Trough samples will be taken pre-morning dose on Days 3, 5, 7, 9, 11, and 13.

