t _{max}	Time to reach maximum (peak) plasma concentration	Obtained directly from the concentration–time data.
Areas under the curve		
λ _z	Terminal rate constant	Estimated by linear regression of logarithmically transformed concentration versus time data.
t _{1/2}	Terminal half-life	Calculated from the terminal slope of the log concentration–time curve, as follows: $t_{1/2} = \frac{\log_e 2}{\lambda_z}$

Text symbol	Definition	Calculation
Areas under the curve (after final dose)		
AUC _{tau}	Area under the plasma concentration–time curve during a dosing interval (tau)	Calculated using the trapezoidal method.
AUC _{last}	Area under the plasma concentration–time curve from time zero to time of last measurable concentration	Calculated using the trapezoidal method.
AUC ₇₂	Area under the plasma concentration–time curve from time zero to time 72 h	Calculated using the trapezoidal method.
AUC _{inf}	Area under the plasma concentration–time curve from time zero to infinity	Calculated using the trapezoidal method for the interval 0 to t _{last} (time t _{last} is the time at which the last non-zero level was recorded), plus the area under the exponential curve from t _{last} to infinity, calculated as follows: $AUC_{t-\inf} = \frac{\hat{C}_t}{\lambda_z}$ where \hat{C}_t is the predicted value of the concentration at t _{last} . $\%AUC_{extrap} = \frac{100 \times AUC_{t-\inf}}{AUC_{\inf}}$
%AUC _{extrap}	Percentage of AUC _∞ extrapolated from t _{last} to infinity	

Days 2–14

Text symbol	Definition	Calculation
Concentrations during and after multiple dosing		
C _{trough}	Trough plasma concentration	Trough plasma concentration (measured concentration at the end of a dosing interval at steady state [taken directly before next administration]) obtained directly from the concentration–time data.

Final dosing day

Text symbol	Definition	Calculation
Concentrations and times (after final dose)		
C _{max}	Maximum (peak) plasma concentration	Obtained directly from the concentration–time data.
t _{max}	Time to reach maximum (peak) plasma concentration	Obtained directly from the concentration–time data.
Half-life (after final dose)		
λ _z	Terminal rate constant	Estimated by linear regression of logarithmically transformed concentration versus time data.
t _{1/2}	Terminal half-life	Calculated from the terminal slope of the log concentration–time curve, as follows: $t_{1/2} = \frac{\log_e 2}{\lambda_z}$

Text symbol	Definition	Calculation

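### The BLQ rules in section 16.1 do not provide for Part C troughs; on their natural reading they drop BLQ troughs and would bias mean Ctrough upward under once-daily or low-dose twice-daily dosing

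*Combined protocol and SAP*

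**What the plan says.** Section 16.1 has two BLQ rules for plasma, and neither is specific to a trial part.

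- **Parameter rule** (all PK parameters and individual plots): BLQ values before tmax "will be taken as zero; all other values will be taken as missing".
- **Summary rule** (descriptive tables of plasma levels): "BLQ values will be taken as zero, unless they fall between two quantifiable concentrations, in which case they will be treated as missing".

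The same section adds: "Missing data will not be imputed".

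Ctrough is a Part C secondary endpoint (sections 2.3.2 and 7.2.2). Section 16.1.1 lists it as a parameter for Days 2–14 and defines it as the "measured concentration at the end of a dosing interval at steady state [taken directly before next administration". In the once-daily schedule (section 12.1.3), "Trough samples will be taken predose on Days 3, 5, 7, 9, 11, and 13". The twice-daily schedule uses the same days, before the morning dose. Section 16.1.1 derives tmax only on Day 1 and the final dosing day.

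On group size, section 8.1.3 says: "At each dose level, 6 subjects will receive BEN8744 and 2 will receive matching placebo". It leaves the choice between once- and twice-daily dosing open.

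**The concern.** Both rules make sense within one single-dose profile. A BLQ value before the peak is a true near-zero, and one in the tail is best left out of the AUC and terminal-slope calculations. A trough is different: a BLQ trough is itself the result, and it says that the concentration had fallen below the assay limit by the next dose.

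If that result is set to missing and not imputed, the subject leaves the Ctrough summary for that day because the value was low. The PK parameter population in section 16.2.3, which keeps only subjects with derivable parameters, does not bring the subject back. The mean and geometric mean are then taken over the higher-exposure subjects only. At stake is an upward-biased summary of a secondary endpoint in a trial whose results will be used to select doses for patient studies (section 6.3).

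**Working it through.** **1. What the rules do to a BLQ trough.** Take a once-daily subject whose troughs are all BLQ and whose Day 1 and Day 14 post-dose samples are quantifiable.

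| Reading | Day 2, 24 h | Days 3–13 | Day 14 predose |
|---|---|---|---|
| Parameter rule, trough set against the tmax of the interval it ends | missing | missing | missing |
| Parameter rule, Day 14 tmax used throughout | zero | zero | zero |
| Parameter rule, each sampling day on its own | missing | undefined (no tmax) | zero |
| Summary rule, over the whole record | missing | missing | missing |
| Summary rule, immediate neighbours only | zero | zero | zero |

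The first row follows the plan's own definition of Ctrough as an end-of-interval value. The fourth is the literal sense of the summary rule, which is not confined to one profile. In the last row, an isolated BLQ trough between two quantifiable samples would still be missing.

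**2. Size when k of 6 troughs are dropped.** Let S be the sum of the measurable troughs and B the unobserved sum of the BLQ ones.

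- Reported mean = S/(6−k). Zero-substituted mean = S/6. Ratio = 6/(6−k).
- True mean of the six = (S+B)/6. Ratio = [6/(6−k)] × S/(S+B), which cannot exceed 6/(6−k).

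For k = 1, 2, 3, 4, 5 the ceiling is 1.2, 1.5, 2.0, 3.0 and 6.0. With k = 6 there is no mean to report.

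**3. Are BLQ troughs plausible?** Section 6.2.4 gives a half-life of about 2–4 h, so 24 h spans 6–12 half-lives and 12 h spans 3–6. Table 2 gives mean Cmax and median tmax. The single-dose concentration at the end of the interval is Cmax × 2^(−(tau − tmax)/t½).

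- 20 mg, 24 h: 46.1 × 2^(−22/2) = 0.02 to 46.1 × 2^(−22/4) = 1.0 ng/mL
- 60 mg, 24 h: 352.83 × 2^(−23/2) = 0.12 to 352.83 × 2^(−23/4) = 6.6 ng/mL
- 6 mg, 12 h: 5.03 × 2^(−10.5/2) = 0.13 to 5.03 × 2^(−10.5/4) = 0.82 ng/mL
- 20 mg, 12 h: 46.1 × 2^(−10/2) = 1.4 to 46.1 × 2^(−10/4) = 8.1 ng/mL

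The LLOQ is not in the documents. The lowest Cmax in Table 2 is 0.59 ng/mL (2 mg), so the LLOQ is assumed to be no higher than that. Even the lowest 20 mg Cmax with a 2 h half-life gives 20.7 × 2^(−5) = 0.65 ng/mL at 12 h, just above that limit.

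**4. Illustrative simulation.** Six subjects, 100,000 runs. Cmax is lognormal from the Table 2 mean and range (log-SD = ln(max/min)/2.534), t½ is uniform on 2–4 h, decline is mono-exponential with linear accumulation, and the LLOQ runs from 0.05 to 0.59 ng/mL. Ratios are to the true mean when BLQ troughs are dropped; runs with no measurable trough are excluded.

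| Dose and interval | Troughs BLQ | Arithmetic mean | Geometric mean |
|---|---|---|---|
| 20 mg once daily | 14–78% | 1.14–2.50 | 1.36–4.06 |
| 60 mg once daily | 1–31% | 1.01–1.39 | 1.02–2.01 |
| 6 mg per dose, twice daily | 4–74% | 1.04–2.44 | 1.09–3.48 |
| 20 or 60 mg per dose, twice daily | at most 0.1% | 1.00 | 1.00 |

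**5. What zero substitution does instead.** Keeping all six subjects with BLQ as zero gives 0.99 down to 0.55 of the true arithmetic mean at 20 mg once daily, and 1.00 down to 0.96 at 60 mg once daily. Zero-filled means are biased low.

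**The case against.** The strongest reply is that this is an ambiguity rather than an error. Section 16.1 does not say which tmax governs a trough, or how far the summary rule reaches when it speaks of two quantifiable values. Some readings give zero. A subject withdrawn before Day 14 may also have no later quantifiable sample, so even the whole-record reading does not drop every BLQ trough. That stands: it is not certain that both rules give missing. But the readings that give zero set aside either the plan's definition of Ctrough or the literal summary rule, and two programmers could follow the text and produce different tables.

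Second, section 6.2.4 says that twice-daily dosing will be required in Part C, and at 20 mg or more per dose the effect is about nil. That also stands. However, sections 8.1.3 and 8.5.4 still permit once-daily dosing, and they allow a first daily dose lower than a dose given in Part A.

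Third, section 16.2.7 reports N, n, median, minimum and maximum, and lists individual values, so lost subjects would be visible. They would be, but the mean would remain biased, and a median over measurable values only would be biased too. The summaries are descriptive, with no hypothesis tested (section 16.2.2), which limits the consequence.

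A reader might infer two further things that the documents do not support.

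- **An artificial fall at Day 14**, with BLQ missing on Day 13 and zero on Day 14. This needs a switch to the Day 14 tmax for the one predose sample. Read over the whole record, the summary rule drops the Day 14 predose value as well.
- **Bias in the trough/IC50 argument of section 6.5.2.** That argument rests on superposition from Part A single-dose profiles. Section 6.5 reports only Cohorts A1–A4 as complete at the time of writing, so Part C trough handling cannot have affected it.

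**Conclusion.** The concern holds in a conditional form. Section 16.1 has no BLQ rule for multiple dosing. The parameter rule on its natural end-of-interval reading, and the summary rule over the whole record, both set BLQ troughs to missing. Mean and geometric mean Ctrough would then be biased upward wherever some but not all of the six active subjects are BLQ, by at most 6/(6−k) for the arithmetic mean.

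The effect is material for once-daily or low-dose twice-daily regimens that the plan still permits, and about nil for twice-daily dosing at 20 mg or more per dose. The simulated sizes are illustrative. They rest on the assumed LLOQ range and half-life distribution, on mono-exponential decline with linear accumulation, and on spread taken from single-dose Cmax. The direction of the bias does not depend on those assumptions.

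**What to change.** In section 16.1, and in the SAP that section 16.2.1 says will be written before database lock:

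- Limit both missing-value rules to BLQ values after tmax within the Day 1 and Day 14 post-dose profiles.
- Keep every predose or trough sample after the first dose, including Day 14 predose, in the Ctrough and concentration summaries, with BLQ set to zero. State that the Day 2 24 h sample counts as a trough for this purpose, while AUC and the terminal slope keep the existing rule.
- Make the median the lead summary and report the number BLQ at each trough day. With six subjects the median averages the third and fourth ordered values, so it does not depend on the substituted value when up to two are BLQ.
- Give the mean with BLQ set to LLOQ/2 as a sensitivity analysis, and state the LLOQ.

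The cost is a short addition to the text and no extra data. The downside is that zero-filled means are biased low, which is why they should not lead. Geometric means cannot be given on days with BLQ troughs unless LLOQ/2 is used.
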